IL 8 plays an important role in acute inflammation because it acts as a potential chemotactic agent and neutrophil activator by activating CXCR1 and CXCR2 (Emadi et al., 2005). The reduced IL 8 response induced by LPS in neutrophils has been confirmed in human whole blood translational and non-animal models. This was achieved by exposing neutrophils in vitro to a pro-inflammatory microenvironment containing N-formyl Met Leu Phe, LPS, or IL 8, resulting in a response accompanied by an increase in cell size and pH that leads to a decrease. The detailed kinetics of this degradation can be shown almost in real time by measuring flow cytometry. Overall, we provide a new mechanistic overview of the interaction between IL 8 and neutrophils and explain how IL 8 changes during systemic inflammation.

Meanwhile, MKK6 phosphorylates another MAPK, p38, which leads to the phosphorylation of MK 2 and stabilizes IL 8 mRNA. The activation of the C/EBP signaling pathway is largely still unknown (Matsushima et al., 2022).

CHAPTER III

RESEARCH METHOD

A. Type of Research The type of research used is Clinical Experimental, designed with a Randomized Controlled Trial double blind, with pre and post test design on samples of patients with persistent allergic rhinitis.

B. Place and Time of Research The research is conducted at the Outpatient Clinic of Ear, Nose, Throat Health Science Surgery at the Sebelas Maret University Hospital and the biomedical laboratory of the Faculty of Medicine UNS for the examination of MDA, NF kB, TNF α , Interleukin 6, Interleukin 8. The research will be carried out after obtaining research approval from the dissertation proposal examination board and the Research Ethics Commission.

C. Subjects/Sample of Research Outpatient patients who have undergone anamnesis and physical examination of ENT.

1. Restriction Criteria **Inclusion Criteria:**

- 1) Patients aged 18 – 60 years who have signed informed consent
- 2) Diagnosed with persistent allergic rhinitis with Skin Prick Test or Positive IgE Examination.

Exclusion Criteria:

- 1) The presence of complications in the nose such as nasal septum deviation, polyps, rhinosinusitis
- 2) Have undergone specific immunotherapy for 2 years
- 3) Use of medications that affect allergy test results: antihistamines, corticosteroids, antihypertensive medications, and decongestants
- 4) Pregnancy and Breastfeeding.

Sample Size

The sample size uses the Frederer formula.

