$$\text{Frederer Formula} = (n - 1) (t - 1) \geq 15$$

Explanation: n: sample size of each group: number of groups

According to the Frederer formula, the number of samples required:

$$(n - 1) (t - 1) \geq 15(n - 1) (3 - 1) \geq 15(n - 1) 2 \geq 152n = 17, n = 8.5$$

The number of samples used must be greater than or equal to 9 samples per group. In this study, 10 test samples will be used in each group. This is done to facilitate the author in data analysis calculations, so the total number of samples used in this study is 40 samples.

Sampling Technique

Randomized Control Trial pre and post-test design. Eligible participants/patients who meet the inclusion and exclusion criteria will be randomized. Participants will be grouped into four groups, namely the control group and the treatment group, and then the outcomes will be observed.

F. Implementation/Research Procedure

1. Recruitment of research subjects and randomizationAll patients with persistent allergic rhinitis, Randomization with closed envelopes, Therapy according to the persistent allergic rhinitis algorithm
2. Source of apple fruit extractApple fruit extract is made in the Pharmacy Laboratory of Muhammadiyah University of Surakarta.

3. Preparation of apple fruit extract Polyphenol extract is derived from the fruit of *Mallus sylvestris* mill obtained from apple farmers in Malang. Dried apples are extracted, and re-extracted twice with 50% ethanol. The obtained material is concentrated using a rotary evaporator (Rotavapor, Buchi Labortechnik AG, Switzerland) in a water bath at 40 °C. Furthermore, the extract is adsorbed using Amberlite XAD 16 resin (Brentag, Essen, Germany), and after the evaporation of ethanol, the collected fraction is dried in a vacuum oven SPT 200 (Zeamil, Krakow, Poland) (Mihailović et al., 2018).
4. Measurement of Malondialdehyde (MDA)Measurement of MDA using the Enzyme Linked techniqueItchy noseClinical symptoms in allergic rhinitis.TNSS Checked on the First day and the 14th dayOrdinalRhinorrheaClinical symptoms in allergic rhinitis.TNSS Checked on the First day and the 14th dayOrdinal.

G. Statistical Analysis

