Statistical analysis was conducted using IBM SPSS Statistics for Windows, version 25.0 (IBM Corp., Armonk, NY, USA). Data normality was evaluated using the Shapiro–Wilk test. For normally distributed and homogeneous data, one-way analysis of variance (ANOVA) was applied. When the data were not normally distributed but homogeneous, the Kruskal–Wallis test was used. Comparisons across three time points were performed using repeated-measures ANOVA, with the Friedman test employed as the nonparametric alternative.

REFERENCE

ARIA (Allergic Rhinitis and its Impact on Asthma). 2019. ARIA guideline 2019: treatment of allergic rhinitis in the German health system. Allergol Select. 2019 Dec 30;3(1):22-50. doi: 10.5414/ALX02120E. PMID: 32176226; PMCID: PMC7066682.

Bjermer, Leif; Westman, Marit; Holmström, Mats; Wickman, Magnus C. (2019). The complex pathophysiology of allergic rhinitis: scientific rationale for the development of an alternative treatment option. *Allergy, Asthma & Clinical Immunology*, 15(1), 24 – . doi:10.1186/s13223-018-0314-1

Dalimartha, S. & Adrian, F. (2013). Fakta Ilmiah Buah & Sayur. Jakarta: Penebar Swadya.

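### Section G's tests across three time points drop any patient missing one value, and no all-randomised analysis set or follow-up rule offsets this

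*Combined protocol and SAP*

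**What the plan says.** Section A of Chapter III describes the trial as "designed with a Randomized Controlled Trial double blind, with pre and post test design". Section G opens with "Statistical analysis was conducted using IBM SPSS Statistics for Windows, version 25.0" and then names two sets of tests.

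- For comparing groups: "For normally distributed and homogeneous data, one-way analysis of variance (ANOVA) was applied" and "When the data were not normally distributed but homogeneous, the Kruskal–Wallis test was used". The outcome and visit are not stated.
- For comparing times: "Comparisons across three time points were performed using repeated-measures ANOVA, with the Friedman test employed as the nonparametric alternative". No group factor or group-by-time term is stated.

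Section G names no analysis population, no missing-data method and no sensitivity analysis.

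On numbers, the sample-size section says "The number of samples used must be greater than or equal to 9 samples per group" and then "In this study, 10 test samples will be used in each group". The step from 9 to 10 is explained by convenience of calculation, not by expected withdrawals. The sampling section says "Participants will be grouped into four groups, namely the control group and the treatment group", and the stated total is 40.

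The legible outcome-table entries in Section F place the TNSS symptom items on day 1 and day 14 and mark them as ordinal. The available text defines no third time point for any outcome and gives no sampling day for the laboratory markers.

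**The concern.** Classical repeated-measures ANOVA and the Friedman test work on one complete row per patient. With no imputation, a patient who has two of three values is removed, and both observed values are lost to that test. Patients who stop because they feel no benefit, or do not tolerate the product, are the most likely to have incomplete rows. Results from completers may therefore describe a selected subset, in a trial with only 10 patients per arm.

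The single-visit group tests are less exposed, but not immune. They use whoever was measured at that visit, and nothing in the available text says that a patient who stops is still measured at the end. The plan therefore does not secure an analysis of patients as randomised.

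**Working it through.** **Step 1. The plan's own sample size.** The rule is (n − 1)(t − 1) ≥ 15. With the document's t = 3, n = 15/2 + 1 = 8.5, rounded up to 9. Ten per group in four groups gives 40. Both figures reproduce. (The formula uses three groups and the design has four. That needs reconciling separately and does not affect this point.) Each arm can lose one patient before it falls below the plan's minimum of 9.

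**Step 2. Who each test keeps**, for an outcome measured at three times, without imputation:

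| Values present | Repeated-measures ANOVA, Friedman | Group test on final values | Group test on change from baseline | Mixed model |
|---|---|---|---|---|
| All three | in | in | in | in |
| First and last | out | in | in | in |
| First and middle | out | out | out | in; the middle value informs the final estimate |
| First only | out | out | out | in, but with no post-baseline information |

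As a check on the first column, a standard repeated-measures ANOVA routine (not SPSS) was given ten patients at three times with one cell removed. It refused the data as unbalanced.

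**Step 3. Expected numbers kept.** The documents give no withdrawal rate. Assume each of two post-baseline visits is missed independently with probability p. A three-time test keeps 40(1 − p)² patients and a final-visit test keeps 40(1 − p). The difference, 40p(1 − p), is the expected number who have a final value but are excluded from the three-time test.

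| p | Three-time test | Final-visit test | Difference |
|---|---|---|---|
| 5% | 40 × 0.9025 = 36.1 | 38.0 | 1.9 |
| 10% | 40 × 0.81 = 32.4 | 36.0 | 3.6 |
| 15% | 40 × 0.7225 = 28.9 | 34.0 | 5.1 |

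**Step 4. Chance that at least one arm falls below 9.** If each patient is usable with probability c, an arm of 10 keeps at least 9 with probability c¹⁰ + 10c⁹(1 − c).

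- Three-time test, p = 10% (c = 0.81): 0.122 + 0.285 = 0.407, so 1 − 0.407⁴ = 0.97.
- Final-visit test, p = 10% (c = 0.90): 0.349 + 0.387 = 0.736, so 1 − 0.736⁴ = 0.71.
- At p = 5% the two figures are 1 − 0.746⁴ = 0.69 and 1 − 0.914⁴ = 0.30.

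Much of the risk therefore comes from missing final values, which no choice of test recovers.

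**Step 5. Possible bias.** This is an illustrative simulation of two arms of 10 at three visits, with unit SD, correlation 0.5 and a true final difference of 0.80 SD. Dropout after the second visit depends on the second score. The comparison method predicts the final value from the two earlier visits within each arm.

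| Assumed dropout | Share lost | Completers only | All observed visits |
|---|---|---|---|
| Same mechanism in both arms | 14% | 0.77 | 0.80 |
| Outcome-related in control only | 13% | 0.70 | 0.80 |
| Opposite mechanisms | 20% | 0.55 | 0.77 |

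The rates and mechanisms are assumptions. The gain in the last column exists only because an intermediate score was observed.

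**The case against.** A reader might infer that the randomised comparison as a whole becomes a completers-only one. The documents do not support that. The Friedman test compares times within patients and compares no arms, and Section G does not give the repeated-measures ANOVA a group term. The group tests in the same section keep a patient who missed only an intermediate visit. For the same reason, loss of collected data is not certain whenever a visit is missed; it depends on which test is used. The 0.97 in Step 4 should not be read as a forecast either, because it rests on assumed independent misses at two post-baseline visits.

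Three further objections carry weight.

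- The legible TNSS schedule has two times. A patient without day 14 then has only a baseline value, and a mixed model gains nothing.
- The TNSS items are ordinal, so a Gaussian mixed model cannot serve every outcome.
- Part of the procedure text in Section F is broken, so the absence of a follow-up rule there can be asserted only for the text available. Section G reads as a complete paragraph, so its silence on missing data is firmer.

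These limit the point without removing it. The three-time tests still need complete rows, and a patient with no final measurement is still lost from the group tests.

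**Conclusion.** The point holds for the tests across three time points: as specified, they use completers only by default. Listwise deletion is not written in the plan; it follows from the named methods together with Section G's silence on missing values. For the single-visit group tests the result is an available-case analysis, which also departs from all randomised patients when final values are missing.

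The size is conditional. It is zero with full follow-up. Under 5% to 15% independent misses per visit, the three-time tests would leave out about 2 to 5 patients of 40 who do have a final value. Bias in the illustration ranged from slight (0.77 against 0.80) to substantial (0.55 against 0.80), depending on why patients leave. This should be corrected, because the trial is small and the remedy is cheap, but it does not by itself invalidate the group comparisons.

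**What to change.** In Section G:

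- Define the three time points for each outcome, and reconcile them with the pre/post design and the day 1 and day 14 TNSS schedule.
- Define an analysis set of all randomised patients in the arm assigned.
- For outcomes measured at three times, replace repeated-measures ANOVA with a linear mixed model for repeated measures: arm, visit and arm-by-visit, fitted by restricted maximum likelihood with small-sample degrees of freedom. Include every randomised patient with any measurement. The MIXED procedure in the named software can fit it.
- Keep a rank-based or ordinal analysis for the ordinal TNSS items and for clearly non-normal markers.
- Report the completers-only analysis as supportive.

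In Section F, state that the final scheduled outcome measurements are taken whether or not the patient is still taking the study product, and that the date and reason for stopping are recorded.

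The cost is wording: no extra scheduled visit, patient or software, although patients who stop must be asked to attend the visit already scheduled. The downside is small. The model assumes that missingness depends only on observed values and that the data are approximately normal, which is hard to verify with 10 per arm.
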